Because it is not feasible to include all components of CBTs for youth anxiety in a SSI, we prioritize evidence-based components that are able to be understood and implemented by families following only a single session. This includes psychoeducation on the cognitive behavioral conceptualization of anxiety, introduction to self-regulation strategies to manage physiological manifestations of anxiety, and cognitive restructuring of anxiogenic thoughts. Given parents' important roles in facilitating implementation and practice of material presented in CBT approaches for youth anxiety (Silverman & Kurtines, 1996), we also will involve parents in the SSI and present strategies on how parents can support their children in managing anxious feelings and thoughts. In designing the module, we will leverage best practices for remotely delivered SSIs, including the use of engaging visual content with corresponding audio and interactive vignettes as well as comprehension checks (Schleider et al., 2020a). Details on the SSI components are provided in Methods.

Specific Aims

We will pursue the following aims in N = 60 families on waitlists for outpatient psychosocial treatment for youth anxiety.

Aim 1 Pilot Phase: Develop and pilot a SSI tailored for families on waitlists for outpatient psychosocial treatment for youth anxiety disorders. We will pilot the SSI with N=5 families and use cognitive response interviewing to obtain data from parents and children, ensuring the content is understandable and accessible. We will refine the SSI based on these data.

Following the Pilot Phase, we will enroll an additional N = 60 families and randomize them to either the SSI (n = 30) or waitlist control (n = 30)

Aim 2 Test Phase Acceptability, and Satisfaction: Examine acceptability of the refined SSI, as well as satisfaction with the SSI. We hypothesize that users will find the module to be acceptable and will report high satisfaction.

Aim 3 Test Phase Anxiety Outcomes: Demonstrate reductions in youth anxiety symptom severity. We hypothesize that anxiety symptom severity and impairment will be significantly lower among youth who receive the refined SSI relative to youth on waitlist control.

Approach

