We will first pilot the SSI with five families and use cognitive response interviewing to obtain data from youth and parents, ensuring that the content is understandable and accessible. The SSI will be refined based on these data. Will then will evaluate the refined SSI in a sample of 60 youth participants and their parents. Participants recruited for this study will be youth 7-17 years old on waitlists at outpatient clinics to receive psychosocial treatment for anxiety disorders. Following an intake evaluation, eligible participants will be randomly assigned to one of two arms: the SSI (n=30) or the waitlist control (n=30).

Inclusion Criteria. (A) Be between ages 7 and 17 years; (B) endorse clinically elevated anxiety symptoms on either parent or youth report, as indicated by a score ≥ 25 on the Screen for Child Anxiety and Related Emotional Disorders-Child or Parent Versions (SCARED-C/P).

Exclusion Criteria. (A) parent report of past diagnosis of Autism Spectrum Disorder, Intellectual Disability, Bipolar Disorder, Tourette's Disorder, Psychotic Disorders, or Substance Use Disorders; (B) show high likelihood of hurting themselves or others; (C) not having access/connectivity needed for telehealth video conferencing to complete the module.

Procedures

Pilot Phase. Because our module integrates existing strategies and content found in evidence-based CBTs (see SSI Module below), our pilot phase prioritizes user experience (youths, parents) over expert content review. We will identify N = 5 families on our waitlist and administer the SSI module content to each youth-parent dyad. In cognitive response interviews, we will use verbal probing to ask youths and parents to provide feedback on module content (e.g., "what strategies do you find most helpful?, "which strategies were more difficult to understand?", "was there anything you disliked about the module?"), duration (e.g., "did you find the length of the module to be appropriate?"), and graphics (e.g., "was the module visually stimulating?", "what would help make module more interesting to view?"). We will use data obtained in these interviews to further refine the SSI module, ensuring clear and simple language that is accessible and engaging to youths and parents.

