Test Phase. Upon contacting our outpatient clinic, parents will complete a screener to assess inclusion/exclusion criteria. Eligible youth and parents will then be presented with web-based assent/consent forms. Families who provide consent/assent will then complete the PRE evaluation consisting of demographics, SCARED-C/P and Child Anxiety Impact Scale – Child and Parent Versions (CAIS-C/P). Following completion of the PRE evaluation, families will be randomized immediately to either the SSI or waitlist control. Parents of the youth randomized to the SSI will receive a secure link via email containing the module and will be instructed to open it immediately. Both parent and youth will participate in the interactive module simultaneously. After completing the SSI, families will be granted access to view the module video an unlimited number of times and access to reference guides that summarize the module content.

Parents and youth will complete a POST evaluation one week after PRE and a Follow-Up evaluation four weeks after PRE. The POST and Follow-Up evaluations will consist of the same measures as the PRE evaluation, plus the Program Feedback Scale (PFS) and Client Satisfaction Questionnaire – 8 (CSQ-8) at POST and the Treatment Utilization Questionnaire at Follow-Up.

SSI Module

The module contains video segments presenting psychoeducation content and evidence-based practices for managing/reducing anxiety. Interactive exercises and comprehension questions are embedded throughout the module to

solidify understanding of concepts and correct misunderstandings. The module includes 4 main elements based on evidenced-based practices for managing/reducing anxiety (Higa-McMillan et al., 2016) and practices in single session intervention design (Schleider et al., 2020a).

- 1. Psychoeducation on the tripartite model of anxiety—how anxiety manifests itself through thoughts, feelings, and behaviors.
- 2. Psychoeducation and practice on self-regulation strategies to manage physiological manifestations of anxiety (i.e., feelings). Families will be introduced to "staying in the moment" and "relaxation strategies" and will have the opportunity to practice implementing the chosen strategy.
- 3. Explanation and practice of cognitive restructuring of anxious thoughts into neutral or realistic thoughts.
- 4. Evidence-based strategies on how parents can support their children in managing their anxious feelings and thoughts.

Measures

Primary Outcome.

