Youth anxiety outcome measure completed by parents and youths. Screen for Child Anxiety Related Emotional Disorders—Child and Parent Versions (SCARED-C/P; Birmaher et al. 1997). The SCARED, child and parent versions, are 41-item rating scales that assess anxiety symptom severity. Items are rated on a 3-point Likert scale ranging from "Not true or hardly ever true" to "Very true or often true".

Primary Outcomes.

Youth anxiety impact measure completed by parents and youths. Child Anxiety Impact Scale – Child and Parent Versions (CAIS-C/P; Langley et al., 2004). The CAIS, child and parent versions, assess the impact of anxiety symptoms on the psychosocial functioning of youth. Items are rated on a 4-point Likert scale from "Not at all" to "Very much."

Intervention Acceptability measure completed by parents. The Program Feedback Scale (PFS; Schleider et al., 2020b). The PFS assess acceptability and user perceptions of web-based single session interventions. Seven items are rated on a 5-point Likert scale, ranging from "1" to "5" and participants are asked to share what the liked and what they would change about the intervention in an open-response format. A mean score of ≥3 indicates acceptability and positive program evaluation.

Treatment Satisfaction measure completed by parents and youths. The Client Satisfaction Questionnaire— 8-item version (CSQ-8; Larsen et al. 1979). The CSQ-8 is a widely used measure of satisfaction with mental health services (Sitzia, 1999).

Treatment Utilization measure completed by parents. Because families sometimes initiate alternative treatments during clinical trials, we will collect data on youths' usage of medication and/or psychosocial treatment at any point during their participation (Kolko, 2000). Additionally, we will collect data on whether or not families opted to remain on the treatment waitlist.

STATISTICAL ANALYSIS PLAN

Data management protocols will be used to ensure data integrity. Missing values will be estimated using full information maximum likelihood where applicable. A Holm modified Bonferroni correction will be used to control experiment wise error rate.

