Aim 1: To examine the influence of the SSI on anxiety and anxiety impact (impairment), we will use two-way analyses of covariance in a structural equation modeling (SEM) framework (Rausch et al., 2003). We will use a maximum likelihood estimator with robust standard errors (MLR) as implemented in the MPlus 8.8 statistical software program. In each model, participant age, treatment condition, and the PRE-score on the outcome variable will be included as covariates. Robust likelihood ratio tests will be used to examine differences between PRE and POST mean scores and POST and FOLLOW-UP mean scores).

Aim 2: To examine acceptability, we will examine total mean scores of parents' responses on the PFS. A mean score \geq 3 indicates acceptability and positive program evaluation. To examine satisfaction, we will examine youth and parent total mean scores on the CSQ-8. Consistent with past studies (Larsen et al., 1979; Smith et al., 2014), we will categorize overall satisfaction ratings as "poor" (score = 8–13), "fair" (score = 14–19), "good" (score = 20–25) and "excellent" (score = 26–32).

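### The tests named for the anxiety outcomes compare time points without mentioning arm, so the SAP does not say which test decides Aim 3's SSI-versus-waitlist hypothesis, and none compares the arms at week 4

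*Combined protocol and SAP*

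**What the plan says.** - **Hypothesis.** Specific Aims, Aim 3, expects severity and impairment to be "significantly lower among youth who receive the refined SSI relative to youth on waitlist control". This is a comparison of arms. No time point is attached to it. The aim's opening words are "Demonstrate reductions in youth anxiety symptom severity", which on their own have no comparator.
- **Model.** The matching SAP paragraph is labelled Aim 1, a clerical mismatch with the protocol's numbering. It begins: "To examine the influence of the SSI on anxiety and anxiety impact (impairment), we will use two-way analyses of covariance". The two factors are not named. It adds that "participant age, treatment condition, and the PRE-score on the outcome variable will be included as covariates".
- **Tests.** The paragraph then names one kind of test: "Robust likelihood ratio tests will be used to examine differences between PRE and POST mean scores and POST and FOLLOW-UP mean scores".
- **Schedule.** Procedures, Test Phase: "Parents and youth will complete a POST evaluation one week after PRE and a Follow-Up evaluation four weeks after PRE".
- **Multiplicity.** The opening of the SAP says "A Holm modified Bonferroni correction will be used to control experiment wise error rate", without listing the tests it covers.

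**The concern.** The hypothesis is about arms and the named tests are about time. Nothing in the SAP says that the treatment-condition coefficient, an arm-by-time term, or an adjusted arm difference at POST or Follow-Up will be tested or will decide Aim 3. Treatment condition appears only in a list of covariates. PRE is both a covariate and one side of a tested contrast, so the named PRE-POST test is not simply the covariance-analysis arm coefficient, and one cannot be inferred from the other.

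Two things are at stake. First, Aim 3 could be reported either from a change over time that both arms share or from the randomised comparison, and the choice could be made after the results are known. Second, Follow-Up data are collected in both arms at four weeks, yet on either reading of the sentence no named test asks whether the arms differ then.

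**Working it through.** The plan states no power, effect size, SD, correlation, alpha or sidedness, so there is no figure of its own to reproduce. The finding rests on the text. The numbers below only show how far the possible readings diverge.

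**Inputs.** From the documents: 30 per arm; PRE, POST (week 1) and Follow-Up (week 4). Assumed: SD 1, normal data, equal correlation r of 0.5, 0.7 or 0.8 between any two time points, two-sided 0.05, no Holm. A paired t-test stands in for the pooled likelihood ratio test.

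**1. Literal reading: a time contrast pooled over arms.** With no SSI effect and the same fall d in both arms, the noncentrality is d × √60 / √(2(1 − r)).
- d = 0.2, r = 0.5: 0.2 × 7.746 / 1.000 = 1.549, rejection 33%.
- d = 0.3, r = 0.8: 0.3 × 7.746 / 0.632 = 3.674, rejection 95%.

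Within the SSI arm alone (√30 in place of √60), the range is about 19% to 71%. In simulation, the arm contrast adjusted for PRE and age rejects in about 5% of the same trials, or 6% to 7% with large-sample robust standard errors as a stand-in for MLR.

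**2. Charitable reading: SSI-minus-waitlist differences in change.** Let e1 and e2 be the SSI effects at POST and Follow-Up. Randomisation makes the expected PRE difference zero.
- PRE-POST estimates e1.
- POST-Follow-Up estimates e2 − e1.
- Their sum is e2, the week-4 effect, but no joint test is named and neither contrast alone estimates e2.

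If a 0.5 SD effect is fully sustained, e2 − e1 = 0 and POST-Follow-Up rejects in about 5%. If the effect has vanished by week 4, e2 − e1 = −0.5 and it rejects in 48%, 69% and 85% (r = 0.5, 0.7, 0.8). It answers a question about maintenance, not about whether the arms differ at week 4.

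**3. An effect that builds: e1 = 0.25, e2 = 0.5.** Each named contrast then has 0.25 SD to detect.
- Standard error of a difference in change: √((2/30) × 2(1 − r)) = 0.258, 0.200, 0.163. Ratios 0.25/SE = 0.97, 1.25, 1.53.
- Approximate standard error of the adjusted arm contrast: √((2/30) × (1 − r²)) = 0.224, 0.184, 0.155. Ratios 0.5/SE = 2.24, 2.71, 3.23.

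Simulated rejection rates (20,000 trials per setting):

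| r | PRE-POST, between arms | POST-Follow-Up, between arms | Either one | Adjusted arm test at Follow-Up |
|---|---|---|---|---|
| 0.5 | 16% | 16% | 31% | 58% |
| 0.7 | 23% | 24% | 45% | 75% |
| 0.8 | 33% | 32% | 60% | 88% |

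**4. Is regression to the mean a source of shared change?** Entry requires families to "endorse clinically elevated anxiety symptoms on either parent or youth report", with a SCARED cut, and SCARED is also an outcome. The order of events matters. Procedures, Test Phase, places an eligibility screener before consent and PRE. If selection is on an earlier screener score s standard deviations above the mean, equal correlations give an expected PRE of r × s and an expected POST of r × s, so the expected PRE-to-POST fall is r × s − r × s = 0. The pooled test then rejects in about 5%. Only if the PRE score itself qualifies the family is there an expected fall, of (1 − r) times the PRE elevation. In that case the pooled test rejects in about 15% to 74% if 50% to 70% of screened families pass the cut, and 7% to 9% if 90% pass (pass rates assumed).

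**The case against.** The strongest reply is that a between-arm test is plainly meant. Aim 3 names the waitlist comparator, the SAP paragraph gives its purpose as the influence of the SSI, the analysis is called two-way (which may mean arm by time), and treatment condition is in each model. The tests sentence also ends in an unmatched closing bracket, so words may have been lost. Much of this stands. A reader might infer that the SAP omits the randomised comparison or plans a pooled before-after analysis. The documents do not support that: the pooled reading is the less likely one, and the opening words of Aim 3 give it only slight support because the next sentence supplies the comparator. What remains is that the deciding test is not stated.

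A second reply is that PRE-POST for the effect and POST-Follow-Up for maintenance is a coherent pair, since the protocol's primary goal is short-term reduction and Aim 3 names no time point. That stands too: POST-Follow-Up is a legitimate maintenance check, and a null result under a sustained effect is what it should give. It is still not a comparison of arms at week 4.

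Third, a reader might infer that the SCARED entry cut makes a spurious fall likely. The documents do not support that as a main route, because the screener precedes PRE. The point is not fully closed: the screener is completed by parents, the criterion also accepts youth report, and the Approach section mentions an intake evaluation before randomisation.

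Finally, the pooled calculation omits the covariates that the SAP puts in its models, so it illustrates the literal wording and not the specified model.

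**Conclusion.** The concern holds as a gap in the stated decision test, and it should be fixed. The model can estimate the arm effect. The sentence naming the tests does not say that this effect is what is tested, and on neither reading does it compare the arms at week 4. This conclusion needs no assumption beyond the text.

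The size does rest on assumptions, because the documents give no SD, correlation, decline or effect. A shared fall of 0.2 to 0.3 SD separates a pooled test (about 33% to 95%) from the adjusted arm test (about 5%), and an effect building to 0.5 SD separates each named contrast (about 16% to 33%) from the adjusted arm test at Follow-Up (about 58% to 88%). The 33% to 95% should not be read as this trial's false-positive rate: it would mislead only if a pooled change were reported as an SSI effect, which the documents do not say will happen.

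**What to change.** Replace the tests sentence with: *Aim 3 is tested by the treatment-condition coefficient (SSI minus waitlist), adjusted for PRE score and age, at POST and at Follow-Up, for SCARED-C, SCARED-P, CAIS-C and CAIS-P; these tests are corrected by Holm. PRE-POST and POST-Follow-Up changes are reported by arm as descriptive or as a maintenance check.*

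If time contrasts are kept as tests, define them as SSI-minus-waitlist differences in change and use PRE-POST and PRE-Follow-Up, so that week 4 is tested. At an assumed 0.5 SD effect these have about 48% to 85% power per test before Holm. Adding arm to the existing two contrasts would settle the ambiguity about arm but would leave week 4 untested. Relabelling the paragraph as Aim 3 is clerical.

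Cost: one SAP sentence, with the same model and data. The number of tests does not rise: 4 scores × 2 contrasts = 8 now, 4 scores × 2 time points = 8 after. The between-arm result may look less favourable than a within-arm change. Power per test at an assumed 0.5 SD effect is about 57% to 88% before Holm, and about 27% to 63% at the strictest Holm step (0.05/8 = 0.00625). The change does not remove the slight excess error of large-sample robust tests at 30 per arm.

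### Does Aim 2 fall short because acceptability is scored from parents only and no CSQ-8 band is named as high?

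*Combined protocol and SAP*

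**What the plan says.** Specific Aims, Aim 2 states: "We hypothesize that users will find the module to be acceptable and will report high satisfaction". It does not define users and gives no threshold for either half.

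Two other places suggest who the users are. Under Procedures, the Pilot Phase text says "our pilot phase prioritizes user experience (youths, parents) over expert content review". The Test Phase text says "Both parent and youth will participate in the interactive module simultaneously".

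Measures heads the PFS entry "Intervention Acceptability measure completed by parents". The scale has seven items rated 1 to 5, and a mean of 3 or more is read as acceptable. The SAP follows this under Aim 2: "we will examine total mean scores of parents' responses on the PFS", with the same benchmark.

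For satisfaction, Measures assigns the CSQ-8 to both informants, and the SAP says "we will examine youth and parent total mean scores on the CSQ-8". Overall ratings are then sorted into poor (8–13), fair (14–19), good (20–25) and excellent (26–32).

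One sentence in the Test Phase text is looser: "Parents and youth will complete a POST evaluation one week after PRE". The next sentence adds the PFS and CSQ-8 at POST without naming who completes each.

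**The concern.** Within one hypothesis, *users* appears to mean two groups for satisfaction and one for acceptability, and no reason is given. A parent PFS mean of 3 or more could be taken as support for a statement about everyone who used the module, although the youths, whose anxiety is the target, were not scored on acceptability. A poor youth reception of the refined module would not show on that scale.

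The satisfaction half has a different gap. The PFS has an explicit cut-off, whereas nothing says whether *high* on the CSQ-8 means good or better, or excellent only. Nor does the SAP say outright whether the bands apply to group means or to each respondent's total. They are whole-number ranges, so a group mean of 25.4 falls in none of them. In principle, a reading of *high* could be chosen after the data are seen.

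**Working it through.** There is no planned figure to reproduce: Aim 2 carries no alpha, power, effect size or SD. The check compares the texts and adds some simple counts.

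**1. Who is scored.** Take 30 SSI families (Approach), each with one youth and one parent, and assume full completion.
- Users: 30 + 30 = 60.
- PFS analysed: 30 of 60, with 0 of 30 youths.
- CSQ-8 analysed: 60 of 60.

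**2. Do the operative sections conflict?** No. Measures names an informant for every scale: SCARED, CAIS and CSQ-8 for both; PFS and treatment utilization for parents. The SAP repeats the parent restriction for the PFS. The POST sentence describes the visit as a whole, and the specific informant statements settle who fills in what. Only the general word in the hypothesis is broader than the measure.

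**3. Could unmeasured youth scores overturn the PFS reading?** With equal numbers, the all-user mean is (P + Y)/2, where P is the parent mean and Y the youth mean. It is below 3 when Y < 6 − P.
- P = 3.5: Y < 2.5
- P = 4.0: Y < 2.0
- P = 4.5: Y < 1.5
- P = 5.0: never, since (5 + 1)/2 = 3.0

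The arithmetic is right but carries little weight. The plan never pools informants, and nothing in the documents suggests youth means that low. The bounds only restate that an unmeasured score could take any value.

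**4. Do the CSQ-8 bands leave gaps?** It depends on the unit.
- Individual totals: the bands hold 6 + 6 + 6 + 7 = 25 whole numbers, and the scale has 32 − 8 + 1 = 25. Every total has exactly one band.
- Group means at n = 30: sums run from 240 to 960, which is 721 values. Those strictly between bands number 3 × 29 = 87, and 87/721 = 12.1%. Means of at least 20 but below 26 have sums 600 to 779, which is 180 values, and 180/721 = 25.0%.

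These percentages give a mean of 8.0 the same weight as one of 25.0, so they say nothing about how likely an awkward result is. The SAP sorts overall satisfaction ratings, which reads naturally as each respondent's total, and on that reading there is no gap.

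**5. Can the choice of band change the word *high*?** Yes, in a limited range. Assume a true mean of 25, n = 30 and an SD of 3 to 6 (none of this mean and SD is in the documents), with SE = SD/√30.
- SD 3: SE = 0.55, P(mean ≥ 26) = 0.03, P(mean ≥ 20) ≈ 1.00.
- SD 6: SE = 1.10, P(mean ≥ 26) = 0.18, P(mean ≥ 20) ≈ 1.00.

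For a group mean from 20 up to just under 26, the label depends on the cut-off. The reported mean and the distribution over bands do not.

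**The case for a change.** The strongest case for a change is that the documents treat acceptability and satisfaction as separate constructs with separate scales, so the youth CSQ-8 cannot stand in for a youth PFS. The pilot interviews do hear from youths, but they involve five families and precede the refinement, whereas Aim 2 concerns the refined module. On this view the plan holds no youth acceptability score for the product under test, and it leaves an interpretive choice open on the CSQ-8. A few sentences would settle both.

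The facts in this stand: the hypothesis is worded more widely than the PFS informant, and no band is designated as high. What does not follow is a defect in the analysis. The SAP ties the PFS result to parents and plans no youth acceptability conclusion. Youths are not absent from Aim 2, because their CSQ-8 scores are analysed alongside the parents'.

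The only remedy that would add information is a youth PFS. It means seven more rated items at a visit where youths already complete three scales, it is possible only for families not yet past POST, and the documents do not say whether the scale suits a 7-year-old. That is a debatable trade, not a correction. The other remedies settle wording and leave every computed quantity as it is.

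**Conclusion.** No change follows. Followed as written, the plan gives a sound descriptive result: a parent PFS mean against a stated benchmark of 3, and youth and parent CSQ-8 scores against bands fixed in advance. The mismatch is one general word in a one-sentence hypothesis, made specific by two later sections that agree with each other. The missing definition of *high* is a gap an analyst fills sensibly by banding each respondent's total and showing youths and parents separately, so that the reader can apply either cut-off.

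The size is small. Half of the SSI-arm users (30 of 60) have no analysed PFS score, all 60 have an analysed CSQ-8 score, and the anxiety and impairment comparison is untouched. This rests on one parent per family, full completion, and a report that presents the PFS result as the parents' rating, as the SAP already does. A report that claimed acceptability among youths from parent scores would overreach, but that would be an error of reporting, not one the plan requires.
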